1.2. ALN-PCS_{SC}, an RNAi Therapeutic for Hypercholesterolemia

ALN-PCS_{SC} Solution for Injection (subcutaneous [SC] use) is comprised of the PCSK9 siRNA, ALN-60212, formulated in phosphate buffer. The PCSK9 siRNA is a chemically synthesized double stranded oligonucleotide covalently linked to a ligand containing GalNAc residues. This synthetic investigational RNAi therapeutic has been designed to suppress the liver production of PCSK9 when administered via SC injection. Inhibition of PCSK9 synthesis through an RNAi mechanism has the potential to lower tissue and circulating plasma PCSK9 protein levels, resulting in higher expression of LDLR in the liver, and consequently lower LDL-C levels in the blood stream. The initial proposed indication for ALN-PCS_{SC} is the treatment of subjects with hypercholesterolemia who are not achieving therapeutic LDL-C goals despite maximally tolerated lipid-lowering therapy, or for subjects who are intolerant of statins.

1.2.1. Nonclinical Studies

The safety pharmacology and toxicology of ALN- PCS_{SC} was evaluated in a series of in vitro and in vivo nonclinical studies.

The drug substance in ALN-PCS_{SC} (ALN-60212) is designed to match the human and cynomolgous monkey mRNA transcripts for PCSK9, sharing a substantial partial match to the rat PCSK9 mRNA. ALN-60212 was informatically identified from a large collection of possible siRNAs targeting PCSK9 based on its predicted potency and selectivity. ALN-PCS_{SC} reduced the expression of PCSK9 in Hep3B liver cells with an IC₅₀ of 20pM and inhibited hPCSK9 serum protein levels in a Tg mouse model with a single dose ED₅₀ of approximately 2 mg/kg and an ED₈₀ dose of approximately 6 mg/kg. In single and multi-dose regimen studies in cynomolgus monkeys, ALN-PCS_{SC} exhibited dose-dependent sustainable suppression of PCSK9 protein that was paralleled by lowering of serum LDL-C with the same kinetics. The time to reach PCSK9 and LDL-C nadir was approximately 20 days and there was no difference in time to nadir between different dose levels. In single dose studies the maximal mean PCSK9 and LDL-C inhibition was 85% and 68%, respectively, which was observed at the two highest doses of ALN-PCS_{SC} administered (6 and 10 mg/kg); however, the duration of PCSK9 silencing and LDL-C lowering was markedly extended at the higher 10 mg/kg dose. In multi-dose studies the maximal mean PCSK9 and LDL-C inhibition was 93% and 74%, respectively, which was similar to those observed in the single dose study. Following discontinuation of ALN-PCS_{SC} administration, recovery of PCSK9 levels was slow, returning to baseline after 100 days in the single dose study and only showing partial recovery between doses in the multi-dose regimen. There were no ALN-PCS_{SC} related changes to the levels of HDL-C or triglycerides in any of the groups. As expected, total cholesterol levels were reduced by up to 30% reflecting the decrease in LDL-C.

Good Laboratory Practice (GLP) compliant repeat dose studies of 4 and 15 weeks duration have been conducted in rats and monkeys. These studies included toxicokinetic analysis of ALN-PCS_{SC} in plasma and in tissues including the liver which is the target organ, and the kidney which is the main organ of elimination.

The GLP 4 week toxicology studies in rats and monkeys involved every other week administration of ALN-PCS_{SC} at dose levels of 10, 50 and 250 mg/kg and once a week administration of 10 mg/kg for rats and 30 mg/kg for monkeys. The GLP 15 week toxicology studies in rats and monkeys involved once monthly administration of ALN-PCS_{SC} at dose levels of 10, 50 and 250 mg/kg and once every other week administration of 125 mg/kg for rats and 25 mg/kg for monkeys. Each toxicology study also included an 8 week treatment free recovery period for all dose groups. ALN-PCS_{SC} was well tolerated in all studies and there were no dose limiting toxicities. The most common findings were related to the pharmacological effects of ALN-PCS_{SC} on lipid profiles. There were consistent decreases in low density lipoprotein cholesterol (LDL-C) and total cholesterol which were expected. Histopathological findings included vacuolation in hepatocytes of rats and lymph node macrophages of monkeys and the presence of basophilic granules in hepatocytes of monkeys and kidneys of rats. These microscopic findings were not associated with changes in clinical pathology parameters and are consistent with class effects of oligonucleotides and were not considered adverse. In a non-GLP dose range finding (DRF) study conducted in monkeys, ALN-PCS_{SC} did not stimulate pro-inflammatory cytokines, activate complement or impact coagulation. ALN-PCS_{SC} also did not stimulate pro-inflammatory cytokines following single dose administration to mice. In a cardiovascular and respiratory study in telemetered conscious cynomolgus monkeys ALN-PCS_{SC} had no immediate or delayed effects on clinical observations, qualitative or quantitative ECG parameters, hemodynamic parameters, respiration rate, or body temperature at any dose level. In addition, ALN-PCS_{SC} did not induce gene mutations or chromosomal damage in a battery of in vitro and in vivo genotoxicity studies.

Further information is in the Investigator's Brochure (IB).

1.2.2. Clinical Studies

One Phase I study has been conducted to date (Study ALN-PCS_{SC} -001). This was a randomized, single-blind, placebo-controlled, single-dose escalation and multiple-dose study of ALN-PCS_{SC} administered SC to subjects with elevated LDL-C. The study was conducted in two phases: a single ascending dose (SAD) phase and a multiple dose (MD) phase. During the SAD phase, 24 subjects were assigned to either receive placebo or one of five doses of ALN-PCS ranging from 25 mg to 800 mg. Those who received doses of at least 100 mg saw their LDL-C drop at least 40%; at the 500 mg dose, LDL-C levels dropped as much as 78%. At 140 days after the treatment was given, subjects still had an average LDL-C reduction of about 40%.

In the MD phase, 45 subjects received multiple doses of either ALN-PCS (125mg weekly x4, 250 mg bi-weekly x2, 300 mg and 500 mg twice given 1 month apart) or placebo. These subjects had maximal LDL-C reductions of 80% and average LDL-C reductions of 50% to 60%. To date, the drug appears to be generally safe and well tolerated. One subject on statin comedication had elevated liver enzymes with ALT >4x the upper limit of normal (ULN), which resolved on stopping the statin.

One Phase II dose finding study (MDCO-PCS-15-01) is currently ongoing. This study is a placebo-controlled, double-blind, randomized trial to compare the effect of different doses of ALN-PCS_{SC} given as single or multiple subcutaneous injections in subjects with high cardiovascular risk and elevated low-density lipoprotein cholesterol (LDL-C). Randomization has been completed and follow up is ongoing. An interim analysis will be performed after all

patients have completed the Day 90 visit in order to select the dose for subsequent studies. A regular review of safety is performed by an independent Data Monitoring Committee and to date no safety concerns have been reported and no changes to the protocol have been requested.

1.2.3. Known and Potential Risks and Benefits

Subjects taking part in this clinical study will receive guideline recommended standard of care as background therapy (including maximally-tolerated statin therapy and/or other LDL-C lowering therapies) when administered ALN-PCS_{SC}. Reduction of LDL-C has been associated with reduced CV risk both by epidemiology and in controlled clinical trials. The safety profile observed to date is considered acceptable for this clinical trial.

An expanded risk-benefit summary is provided in the IB.

1.3. Study Rationale

Homozygous Familial Hypercholesterolemia (HoFH) is a rare and life-threatening disease characterized by markedly elevated circulating levels of low-density lipoprotein cholesterol (LDL-C) and accelerated, premature atherosclerotic cardiovascular disease (ACVD). The first major CV events often occur during adolescence, although angina pectoris, myocardial infarction and death have been reported in early childhood. Historically thought to affect one in a million, new research indicates that HoFH prevalence is likely to be higher, with as many as one in 160,000 to 300,000 people affected. There may be as many as 40,000 people world-wide with HoFH. Due to the severity of the condition, early diagnosis and initiation of lipid-lowering treatment is critical. However, even at the highest doses of the most efficacious statins, only modest reductions in LDL C plasma levels, of 10-25%, are observed. Combination of statin plus ezetimibe can produce a further decrease in LDL-C levels of 10-15%. Combination with other lipid-lowering treatments such as ALN- PCS_{SC} may therefore provide an important adjunctive therapy in HoFH [Cuchel et al 2014].

Previous studies using PCSK9-targeting siRNAs formulated in LNPs (ALN-PCS02) or using PCSK9 antibodies, and one Phase I study with ALN-PCS_{SC} in which subjects received single-doses ascending from 25 mg to 800 mg, have demonstrated that substantial lowering of PCSK9 is safe and well-tolerated in humans. Doses for the Phase I study were calculated using the rat and monkey NOAELs based on body weight and body surface area (mg/m²). Collectively, the results of nonclinical studies with ALN-PCS_{SC} supported a starting dose of 25 mg for subjects participating in the SAD phase of the previous Phase I study.

In Phase I Study ALN-PCS_{SC}-001, clinically significant reductions in LDL-C levels were seen with single ALN-PCS_{SC} doses as low as 25 mg with larger decreases seen with higher doses and a plateau at 300 mg. Subjects at ALN-PCS_{SC} doses of 300 mg or higher had maximal LDL-C reductions of up to 78.1% and average least squares mean group nadir reductions of 50 to 59%. In the MD phase, 45 subjects received multiple doses of either ALN-PCS (125 mg weekly x4, 250 mg biweekly, 300 mg and 500 mg twice given 1 month apart) or placebo. Subjects at ALN-PCS_{SC} doses of 300 mg or higher had maximal LDL-C reductions of 83% and average least squares mean group nadir LDL-C reductions of 53.4% to 59.9% at all dose levels tested.

Based on the interim results of the Phase I Study ALN-PCS_{SC} -001, where maximum effect on LDL-C was seen by 84 days and a significant effect was still observed at 180 days, this study has

been designed to test the efficacy and duration of effect of 300mg of ALN- PCSSc in subjects with HoFH. This will allow dose selection for a subsequent Phase III study in HoFH. The dosing regimens used in this study are therefore fully supported by the findings of the Phase I study.

1.4. Study Population

This study will enroll male and female subjects, ≥ 12 years of age with a diagnosis of homozygous familial hypercholesterolemia.

2. TRIAL OBJECTIVES AND PURPOSE

2.1. Primary Objective(s)

To characterize the effect of 90 and 180 days of subcutaneous ALN-PCS_{sc} on the percentage change from Day 1 in low-density lipoprotein cholesterol (LDL-C) in subjects with homozygous familial hypercholesterolemia

2.2. Secondary Objective(s)

- To assess the effect of ALN-PCS_{sc} on:
 - Absolute change and percentage change in LDL-C from Day 1 to each subsequent visit until Day 180 or final visit
 - Absolute change and percentage change in PCSK9
 - Absolute change and percentage change in total cholesterol, triglycerides, HDL-C, non-HDL-C, VLDL-C, Apo-A1 Apo-B and Lp(a) from Day 1 to each subsequent visit until Day 180 or final visit
- To evaluate the safety and tolerability of ALN-PCS_{sc} in subjects with homozygous familial hypercholesterolemia

2.3. Exploratory Objective(s)

- To evaluate the formation of Anti-drug antibodies (ADA) to ALN-PCS_{sc}
- To assess response of LDL-C by underlying causal mutations of HoFH

3. TRIAL DESIGN

3.1. Type/Design of Trial

This study will be a Phase II, open label, single arm, multicenter pilot study in subjects with homozygous familial hypercholesterolemia. Informed consent (and verbal assent if subject is < 18 years of age) will be obtained from subjects before the initiation of any study-specific procedures.

Subjects who meet study inclusion/exclusion criteria will be instructed to continue to follow a National Cholesterol Education Program (NCEP) Adult Treatment Panel III (or comparable) diet [[Appendix C](#)] and will be required to maintain their current lipid lowering drug therapy for the duration of the study.

In this study, 8-10 subjects will be enrolled and receive open label ALN-PCS_{sc} 300mg SC. Dosing interval will be determined by PCSK9 level at Day 60 or 90 or rate of change of PCSK9 between Days 60 and 90.

On Day 1, eligible subjects will be enrolled and receive the first SC administration of ALN-PCS_{sc}. After first study drug administration, the subject will be observed in the clinic for at least 4 hours post injection before being discharged. Subjects will return at Day 14 and Day 30 and then at monthly intervals. If a second dose of study drug is deemed necessary (if mean serum PCSK9 levels are not suppressed by > 70% at Day 60 or 90, as compared to baseline), subjects will receive this dose at Day 90 or 104 respectively, based on PCSK9 levels from the previous visit.

Study visits will include collection of AE and SAE data, vital signs, ECGs, concomitant medication, and laboratory tests. See [Section 6.1](#) for a detailed list of assessments. The study also includes collection of biomarker samples and, where approved by the independent ethics committee and/or institutional review board (IEC/IRB) and applicable regulatory and other authorities, all subjects will be invited to consent to pharmacogenetics analyses, unless underlying causal mutations of HoFH are well documented by a validated specialized laboratory.

Efficacy assessments will include measurement of the effects of ALN-PCS_{sc} on levels of LDL-C, other lipoproteins including total cholesterol (TC), triglycerides, high-density lipoprotein cholesterol (HDL-C), non-HDL-C, very low-density lipoprotein cholesterol (VLDL-C), apolipoprotein A1 (Apo-A1), apolipoprotein B (Apo-B), lipoprotein(a) [Lp(a)], and PCSK9.

Formation of anti-drug antibodies (ADA) will be assessed on Day 1 (prior to and 4 hours after the injection) and on subsequent visits until the end-of-study (EOS).

[figure not shown]
The EOS visit and the last estimation of lipids will occur at Day 180. Following Day 180 subjects will continue in the study until the observed LDL-C reduction is less than 20% of the absolute reduction from baseline to Day 90. Subjects will be encouraged to complete all planned visits.

The decision to initiate a Phase III study will be defined as an observed mean 15% or greater reduction in LDL-C. A number of factors may influence the proportion of subjects achieving this metric, in particular the specific LDL receptor mutation(s) or other causative mutations of HoFH

studied. Given the small sample size for this part of the study, such issues will be taken into careful consideration prior to making the final decision.

The efficacy and safety/ tolerability data from this study will be reviewed by a Safety Committee (SC) on an ongoing basis, and the results will be used to guide the decision to initiate a Phase III study. A recommendation may be taken to stop or amend the study at any of these reviews.

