6.1. Schedule of Events/Assessments

Study Day	Screening	Treatment Phase								End of Study (EOS)	Additional Follow-Up ^p
	-28 to -1	Day 1	FU1 Day 14 (± 2d)	FU2 Day 30 (± 3d)	FU3 Day 60 (± 3d)	FU4 Day 90 (± 3d) Dose 2? ^a	FU4X Day 104 (± 3d) Dose 2? ^a	FU5 Day 120 (± 3d)	FU6 Day 150 (± 3d)	FU7 Day 180 (± 3d)	FU8 (Day 210) (± 3) FU9 (Day 240) (± 3) FU10 (Day 270) (± 3) FU11 (Day 300) (± 3)
Informed consent	X										
Medical History and prior meds	X										
Physical Examination & full neurologic exam	X									X	
Inclusion / Exclusion Criteria	X	X									
Pharmacogenetic sample ^o	X										
Enrollment		X									
Vital Signs ^b	X	X	X	X	X	X	X	X	X	X	
12 Lead ECG ^c		X								X	
Hematology, Coagulation ^{d, f}	X	X	X	X	X	X	X	X	X	X	X
Biochemistry, Inflammatory markers ^{d, f}	X	X	X	X	X	X	X	X	X	X	X
HbA1c	X	X				X				X	X ⁿ
Urinalysis ^e	X	X ^g								X	X
Pregnancy test ^{e, h}	X	X ^h	X	X	X	X ^h	X ^h	X	X	X	X ⁱ
ADA antibodies ^j		X ^{j, k}		X					X ^k	X ^k	X ^k
Lipids / lipoproteins ^m	X	X	X	X	X	X	X	X	X	X	X
Biomarker (stored samples) ^q	X	X	X	X	X	X	X	X	X	X	X
Study drug admin		X				X ^a	X ^a				
Concomitant medications	X	X	X	X	X	X	X	X	X	X	X
AE reporting		X	X	X	X	X	X	X	X	X	X
SAE reporting		X	X	X	X	X	X	X	X	X	X

ADA = anti-drug antibodies; AE = adverse event; ECG = electrocardiogram; FU=follow-up; EOS = end of study; hsCRP=high sensitivity C-reactive protein; IL6=interleukin 6; IFN- γ =interferon gamma; LDL-C = low-density lipoprotein cholesterol; PCSK9 = proprotein convertase subtilisin/kexin type 9; SAE = serious adverse event; TNF- α =tumor necrosis factor alpha.

- ^a Day 104 visit only for those subjects who receive a second dose of study drug. Dose #2 may be given at Day 90 or 104 depending on PCSK9 levels as compared to baseline
- ^b Vital signs: blood pressure and heart rate will be measured prior to injection and at 4 hours after injection.
- ^c ECG is performed prior to the injection on Day 1.
- ^d Hematology, chemistry (including lactate, bicarbonate, glucose, HbA1c, liver and renal function, hsCRP, IL6, IFN- γ , and TNF- α), and coagulation testing. Blood samples for determination of laboratory values will be performed prior to study drug injection where relevant. All laboratory testing will be performed with subjects in a fasted state.
- ^e Lab tests performed in participating institution's laboratory. Results must be available before the start of study drug injection on Day 1 to confirm subjects meet eligibility criteria.

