- ^f Lab tests performed by study's designated Central Lab facility from enrollment to EOS. In addition, subjects in whom LDL-C reduction is less than 20% of the absolute reduction from baseline to Day 90 will continue to be followed up on a monthly visit schedule either until this level has been reached or until Day 300.
- ^g Urinalysis collection is prior to the injection on Day 1.
- ^h Urine pregnancy test performed at each visit for females of childbearing potential. In addition, postmenopausal women who are less than 55 years of age will have a pregnancy test within 24 hours of enrollment and prior to any study drug injection. Results must be available prior to the injection on Day 1 and, if a second dose of study drug is required, on Day 90/104.
- ⁱ Females of childbearing potential will have a pregnancy test at each additional follow-up visit until LDL-C reduction is less than 20% of the absolute reduction from baseline to Day 90.
- ^j Two ADA samples will be drawn on Day 1: one before the injection and one 4 hours after the injection.
- ^k Additional aliquots of plasma and serum will be collected at each time point and stored for future analyses.
- ^l For subjects in whom LDL-C reduction is less than 20% of the absolute reduction from baseline to Day 90, formation of ADA will be assessed at the last visit.
- ^m Efficacy parameters (Lipids / lipoproteins) will include LDL-C, total cholesterol, triglycerides, HDL-C, non-HDL-C, very low-density lipoprotein (VLDL-C), apolipoprotein A1 (Apo-A1), apolipoprotein B (Apo-B), lipoprotein(a) [Lp(a)], and PCSK9.
- ⁿ Day 270 only.
- ^o Sample may be taken during screening or anytime during study to be processed and stored, but only after separate consent has been signed.
- ^p Additional Follow-Up visits only for those subjects in whom LDL-C reduction is less than 20% of the absolute reduction from baseline to Day 90.
- ^q 3 aliquots of plasma and 3 aliquots of serum will be stored for efficacy and safety biomarker analysis if needed. All samples will be destroyed 1 year following the last subject's last visit in the study.

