6.5. Follow-up Visits FU 1-6

Subjects will return to the study center after study drug administration for Follow-Up Visits according to the Schedule of Events/Assessments ([Section 6.1](#)) until the end of the study.

Procedures will be as follows:

1. Vital signs (blood pressure and heart rate will be measured prior to injection and at 4 hours after injection)
2. Blood samples drawn for clinical laboratory tests:
 - a. Biochemistry
 - b. Inflammatory markers
 - c. Lipids/lipoproteins
 - d. Hematology
 - e. Coagulation
 - f. HbA1c (only at Days 90 and 180 and Day 270 if applicable)
 - g. Anti-ALN-PCSSC (ADA) antibodies (only at Day 30 and Day 150)
 - h. Biomarkers (stored samples)
3. Urine pregnancy test (local) for females of childbearing potential. In addition, on Day 90 or 104 (if a second dose of study drug is required), postmenopausal women less than 55 years of age will have a pregnancy test and results must be available prior to the injection
4. Concomitant medications
5. AE reporting
6. SAE reporting
7. Study drug administration **ONLY** for subjects requiring a second dose of study drug (depending on the degree of suppression of serum PCSK9 as compared to baseline).

If a second dose is deemed necessary, the subject will receive the injection (SC) at **Day 90 or 104**, based on the PCSK9 levels from the previous visit. The site of injection is the abdomen (on the opposite side than the injection on Day 1). The injection site will be marked and mapped for later observation

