6.7. Additional Follow-Up Visits (FU 8-11, if needed)

These visits are only for those subjects in whom LDL-C reduction is less than 20% of the absolute reduction from baseline to Day 90. Procedures will be as follows:

1. Blood samples drawn for clinical laboratory tests:
 - a. Biochemistry
 - b. Inflammatory markers
 - c. Lipids/lipoproteins
 - d. Hematology
 - e. Coagulation
 - f. HbA1c (only at Day 270)
 - g. Anti-ALN-PCSSC (ADA) antibodies (only at last visit)
 - h. Biomarkers (stored samples)
2. Urinalysis (local)
3. Urine pregnancy test (local). Females of childbearing potential will have a pregnancy test at each additional follow-up visit until LDL-C reduction is less than 20% of the absolute reduction from baseline to Day 90
4. Concomitant medications
5. AE reporting
6. SAE reporting

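### Antibody sampling is described as continuing through follow-up, but none is scheduled between Day 30 and Day 150, so in a re-dosed subject a first positive at Day 150 or later cannot be placed before or after the second injection

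*Protocol*

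**What the plan says.** **Summary text.** Protocol 3.1 places ADA assessment on Day 1 "prior to and 4 hours after the injection) and on subsequent visits until the end-of-study (EOS"), excepting no visit. The synopsis and SAP 1.1 say the same.

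**Schedule and visit lists.** Protocol 6.5 limits the sample at FU1-6: "Anti-ALN-PCSSC (ADA) antibodies (only at Day 30 and Day 150"). SAP 2.3 carries the same restriction. The ADA row in protocol 6.1 and SAP Table 1 is marked at Day 1, Day 30, Day 150, Day 180 and additional follow-up, and is blank at Days 14, 60, 90, 104 and 120. On Day 1 there are two draws: "Two ADA samples will be drawn on Day 1: one before the injection and one 4 hours after the injection". In additional follow-up, protocol 6.7 has "Anti-ALN-PCSSC (ADA) antibodies (only at last visit").

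**Second dose.** Footnote a of the schedule says: "Dose #2 may be given at Day 90 or 104 depending on PCSK9 levels as compared to baseline".

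**Stored samples.** Plasma and serum aliquots are kept at every visit, including Days 60, 90, 104 and 120, for biomarker analysis should it be needed. They are destroyed one year after the last subject's last visit (protocol 6.1, footnote q). Neither document plans to test them for ADA.

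**Status of the endpoint.** ADA formation is an exploratory objective and endpoint (protocol 2.3 and 3.5; SAP 1.2 and 5.3.6.3). ADA results also belong to the safety summary (protocol 10.4.4, SAP 5.3.7).

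**The concern.** There are two linked problems.

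First, a reader of the summary text would expect antibody results throughout follow-up, while a site following the schedule would produce none for four months. The SAP repeats both descriptions, so it does not settle which is intended.

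Second, the unsampled interval spans both visits at which a second injection can be given. Re-exposure is when antibody status is most informative, and it is not measured there. Injection site reactions are the adverse event of special interest, and possible anaphylaxis is assessed against formal criteria (protocol 8.2.3). If a re-dosed subject had a reaction, or a weaker LDL-C response, after the second injection, the scheduled samples could not relate it to antibody status at that injection. The trial has 8 to 10 subjects, so one subject whose conversion cannot be dated is 10% to 12.5% of the sample (1/10 to 1/8).

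**Working it through.** The plan gives no figure to reproduce. The check is a comparison of visits and a count of days.

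**Inputs** (protocol 6.1, repeated in SAP Table 1): ADA at Days 1, 30, 150 and 180; second injection at Day 90 or 104; window of ±3 days at Days 30, 90, 104 and 150.

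**Visits without an ADA sample, after Day 1 and through Day 180**
- With the Day 104 visit: 14, 30, 60, 90, 104, 120, 150, 180 = 8 visits. ADA is drawn at 3 (30, 150, 180), so 8 − 3 = 5 have none.
- Without the Day 104 visit: 7 − 3 = 4 have none.

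**Length of the gap**
- Nominal: 150 − 30 = 120 days.
- Shortest: (150 − 3) − (30 + 3) = 114 days.
- Longest: (150 + 3) − (30 − 3) = 126 days.

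**Position of the second injection in the gap**

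| Second dose | Since last ADA sample (Day 30) | To next ADA sample (Day 150) |
|---|---|---|
| Day 90 | 90 − 30 = 60 days (54 to 66) | 150 − 90 = 60 days (54 to 66) |
| Day 104 | 104 − 30 = 74 days (68 to 80) | 150 − 104 = 46 days (40 to 52) |

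The ranges in brackets add and subtract 3 + 3 = 6 days, one window at each end.

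**Which result patterns are affected**
- One dose only: there is no second injection to place a positive against. Not affected.
- Re-dosed and already positive at Day 30: formation precedes the second injection. Not affected.
- Re-dosed, negative at Day 30, first positive at Day 150 or Day 180: the change could have occurred in the 60 or 74 days before the second injection, or after it. The scheduled samples do not separate these. Affected.
- Any re-dosed subject: ADA status on the day of re-exposure is not measured by a scheduled sample.

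**How many subjects.** The documents do not forecast how many will be re-dosed. The number could be anywhere from none to all 8 to 10.

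**The case against.** The strongest reply is that the wording conflict is mild and little depends on the gap. The summary text does not say every visit; where the protocol means that, as for lipids in section 2.2, it uses the word each. Section 3.1 sends the reader to section 6.1 for the detailed list, and the schedule and visit lists agree with one another through Day 180. ADA is exploratory in a descriptive pilot, and neither document plans to analyse it by dose, by reaction or by LDL-C response. Stored aliquots at Days 60, 90 and 104 could be tested afterwards; protocol 7.1.6 allows their use for clinically indicated efficacy or safety analyses. This stands as an argument for low severity. It does not remove the gap: rescue through the aliquots is possible but unplanned and time-limited, and loose wording that appears in three places still needs correcting.

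Several stronger readings are tempting, and the documents do not support them:
- A reader might infer that no ADA sample precedes the second injection. Three do: two on Day 1 and one at Day 30. What is missing is a sample on the day of re-dosing or in the roughly 60 to 74 days before it.
- A reader might infer that no later positive can be interpreted. Only the pattern identified in the working is affected, and that group may be empty.
- A reader might call the 4-hour sample on Day 1 wasted and want it moved. The documents do not state its purpose, and closing the gap does not depend on it.
- A reader might see a conflict over ADA at FU8-11. Those visits share one column, and section 6.7 and footnote l both specify the last visit. The apparent absence of that footnote's mark from the table may come from text extraction.

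**Conclusion.** The point holds as a minor one. In both documents the summary description of ADA sampling does not match the schedule. The schedule leaves 120 days (114 to 126) without an ADA sample, across the only visits at which a second injection can be given. The consequence is confined to re-dosed subjects: their antibody status at re-exposure is unknown, and a first positive at Day 150 or later after a negative at Day 30 cannot be dated relative to the second injection unless stored aliquots are tested.

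This assumes that sites follow the schedule and visit lists rather than the summary text, and that at least one subject is re-dosed. The primary endpoint and the Phase III decision criterion are not affected.

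**What to change.** 1. Add an ADA test on a sample drawn before the injection at the visit where the second dose is given (Day 90 or Day 104). Alternatively, pre-specify in the SAP that the serum aliquot already stored at that visit will be tested for ADA. If the aliquot is used, state that it is drawn before the injection and test it before the one-year destruction date.
2. In the synopsis, protocol 3.1 and SAP 1.1, replace the general reference to later visits with the actual list: Day 1 (before injection and at 4 hours), Day 30, the re-dosing visit if there is one, Day 150, Day 180 and the last additional follow-up visit.

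The 4-hour sample on Day 1 can stay.

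The cost is about one extra assay per re-dosed subject, so between 0 and 10 assays in total, plus a small text amendment. No new visit is needed, because blood is already taken at both visits. The added test would date a conversion as before or after re-exposure. It would not prove which dose caused it: after a negative pre-injection result, late formation in response to the first dose would still be possible.
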